6. MILESTONES

Milestone	Planned date
Start of data collection	06 March 2023
End of data collection	30 October 2024
Final study report	30 October 2024

7. RATIONALE AND BACKGROUND

Human immunodeficiency virus (HIV) infection leads to extensive defects in the immune system, including the progressive depletion and dysfunction of CD4⁺ T cells, perturbation of the B cell compartment with reduced resting memory B cells, and suboptimal humoral immune responses [11-14]. People living with HIV (PLWH) are at increased risk of pneumococcal infections. While antiretroviral therapy (ART) can restore the immune system and consequently lower the risk of pneumococcal infections [2, 15], the burden of pneumococcal infections persists in PLWH [16, 17]. A recent meta-analysis shows that in the era of advanced ART, the incidence rate of invasive pneumococcal disease (IPD) in PLWH is approximately 30 times higher when compared with the general population [1]. Even with timely and effective treatment, the case fatality rate of IPD is at least 8% in PLWH [2]. Up to 25% of PLWH experience recurrent episodes of IPD in the subsequent 12 months [3].

International guidelines recommend pneumococcal vaccination for immunocompromised individuals [4]. In the United States, one dose of 13-valent pneumococcal conjugate vaccine (PCV13) has been recommended to PLWH since 2012 [18]. Currently, the CDC recommends 20-valent pneumococcal conjugate vaccine (PCV20) alone or 15-valent pneumococcal conjugate vaccine (PCV15) followed by pneumococcal polysaccharide vaccine (PPSV23) for adults aged 19-64 years with certain underlying medical conditions, including HIV infection, and for all adults aged ≥ 65 years [19].

Previous research has shown that PCV13 is safe and immunogenic in adults, including PLWH [5-8]. A few studies also assessed the clinical efficacy/effectiveness of a PCV in adults. In a large, randomized, placebo-controlled clinical trial (CAPiTA) of over 84,000 Dutch adults aged ≥ 65 years, PCV13 showed efficacy against both vaccine-type (VT) IPD (VE 75%; 95% confidence interval [CI]: 41% to 91%) and VT non-bacteremic pneumococcal community-acquired pneumonia (CAP) (VE 45%; 95% CI: 14%-65%) [9]. PCV13 efficacy persisted throughout the clinical trial (mean follow-up: 4 years) [9]. A population-based, test negative design, surveillance study reported a PCV13 VE of 73% (95% CI: 13%-92%) against VT CAP in hospitalized adults aged ≥ 65 years [10]. In a clinical trial conducted in HIV-infected adults in Malawi recently hospitalized with pneumonia, two doses of PCV7 demonstrated substantial protection against recurrent pneumococcal infection caused by vaccine serotypes or serotype 6A (VE 74%; 95% CI: 30%-90%) [3], although there was no protection against mortality.

Although the CAPITA study provides important information on PCV13 VE in adults, patients with any immunocompromising condition or treatment were excluded from the study. In contrast to CAPITA, the study by McLaughlin et al. included immunocompromised adults; however, PCV13 VE was reported for the entire study population [10]. Thus, there is a lack of data on PCV13 VE specific to immunocompromised adults. In the absence of such data, in a CDC cost-effectiveness

PFIZER CONFIDENTIAL

model, it was assumed that PCV13 VE in immunocompromised adults was 25% (95% CI: 14%-30%) against VT IPD and 15% (95% CI: 5%-22%) against VT pneumonia, both of which are approximately one third of the VE measured in healthy adults/adults with chronic medical conditions [20, 21].

There has been a longstanding recommendation for pneumococcal vaccination for PLWH in the United States. PCV13 was recommended for PLWH in 2012 and the uptake in PLWH is higher compared with individuals with other risk conditions [22, 23]; this allows us to examine PCV13 VE in the PLWH population over time. Given the lack of PCV13 VE data in immunocompromised adults, this study was designed to estimate PCV13 VE against pneumococcal disease in PLWH aged ≥ 18 years, overall and, if feasible, at 3, 5, and 7 years after vaccination. In addition to IPD and pneumococcal pneumonia, we will include all-cause pneumonia as a disease endpoint in the analysis, because *S. pneumoniae* is the most common bacterial cause of all-cause pneumonia [24].

8. RESEARCH QUESTION AND OBJECTIVES

The primary objectives of this study are:

1. Estimate VE of PCV13 for IPD among PLWH ≥ 18 years of age, overall and, if feasible, at 3, 5, and 7 years of follow-up
2. Estimate VE of PCV13 for pneumococcal pneumonia among PLWH ≥ 18 years of age, overall and, if feasible, at 3, 5, and 7 years of follow-up
3. Estimate VE of PCV13 for all-cause pneumonia among PLWH ≥ 18 years of age, overall and, if feasible, at 3, 5, and 7 years of follow-up

The secondary objectives of this study are:

1. Estimate VE of PCV13 for pneumococcal pneumonia or pneumonia with unspecified causes among PLWH ≥ 18 years of age, overall and, if feasible, at 3, 5, and 7 years of follow-up
2. Estimate VE of PCV13 for pneumonia with unspecified causes among PLWH ≥ 18 years of age, overall and, if feasible, at 3, 5, and 7 years of follow-up

9. RESEARCH METHODS

9.1. Study Design

The VE study will be a retrospective cohort study using health care administrative claims and laboratory data (Figure 1).

PLWH will be identified using administrative claims and include individuals with at least one inpatient International Classification of Diseases, Ninth Revision, Clinical Modification (ICD-9-CM) or International Classification of Diseases, Tenth Revision, Clinical Modification (ICD-10-CM) code related to HIV (Appendix Table 1) or at least 2 outpatient ICD-9-CM or ICD-10-CM codes related to HIV at least 30 days, but no more than 730 days apart, during January 1, 2014 and

PFIZER CONFIDENTIAL

December 31, 2021. PLWH are required to have at least six months of continuous enrollment in one or more health plans and pharmacy benefits after their first HIV-related ICD-9-CM or ICD-10-CM code. These six months of continuous enrollment will be considered the baseline period, during which baseline covariates including demographics, comorbidities, and preventative care will be measured. The baseline period was also selected to minimize the number of outcome events that existed prior to or triggered an HIV diagnosis.

The date following the last date of the baseline period will be defined as the index date. The end of the study will occur on the last date that administrative claims data will be available, September 30, 2022.

For PLWH who receive PCV13 after their index date, we will include the time between their index date and the 13 days after their PCV13 vaccination date as unvaccinated follow-up time. Any outcomes occurring during this time will be counted as events in the unvaccinated cohort. Follow-up that occurs 14 days or more after PCV13 vaccination will be defined as vaccinated follow-up time.

Unvaccinated (no PCV13) PLWH will be followed from index date until the earliest occurrence of the following: 13 days after PCV13 vaccination, death, end of health plan enrollment, or end of study period. Vaccinated PLWH will be followed from 14 days after their PCV13 vaccination, or index date if they were vaccinated during the baseline period, until the earliest occurrence of the following: death, end of health plan enrollment, or end of study period.

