9.2.1. Inclusion Criteria

To be eligible for the vaccine effectiveness study, individuals must meet the following criteria:

1. HIV infection defined as at least one inpatient International Classification of Diseases, Ninth Revision, Clinical Modification (ICD-9-CM) or International Classification of Diseases, Tenth Revision, Clinical Modification (ICD-10-CM) code related to HIV (Appendix Table 1) or ≥ 2 outpatient ICD-9-CM or ICD-10-CM codes related to HIV at least 30 days, but no more than 730 days apart, during January 1, 2014 and December 31, 2021

AND

2. At least 18 years of age at the time of the first recording of HIV-related ICD-9-CM or ICD-10-CM code

PFIZER CONFIDENTIAL

CT24-WI-GL02-RF02 5.0 Non-Interventional Study Protocol Template For Secondary Data Collection Study 01-Aug-2023

AND

[figure not shown]
3. At least six months of continuous enrollment in medical and pharmacy plans after the first HIV-related ICD-9-CM or ICD-10-CM code between January 1, 2014 and December 31, 2021. A gap of 30 days or less in enrollment will be allowed during this six month period.

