9.3. Variables

Table 1. Variables, definitions, and measurement periods

Variable type	Variable	Definition	Measurement period
Exposure	PCV13 vaccination	Current procedural terminology® (CPT) codes and National Drug Codes (NDC) listed in Appendix Table 3	Follow-up
Primary outcomes	IPD	ICD-9-CM or ICD-10-CM codes listed in Appendix Table 4	Follow-up
	Pneumococcal pneumonia	ICD-9-CM or ICD-10-CM codes listed in Appendix Table 4	Follow-up
	All-cause pneumonia	ICD-9-CM or ICD-10-CM codes listed in Appendix Table 4	Follow-up
	Pneumococcal pneumonia or pneumonia with unspecified causes	ICD-9-CM or ICD-10-CM codes listed in Appendix Table 5	Follow-up
	Pneumonia with unspecified causes	ICD-9-CM or ICD-10-CM codes listed in Appendix Table 5	Follow-up
Covariates	Age	Calculated as [year individual meets HIV criteria] – [birth year] Categorized as 18-49, 50-64, 65-74, and ≥ 75 years	Baseline
	Sex	Male, Female, Other, Unknown	Baseline
	Social Vulnerability Index (SVI)	SVI characterizes resiliency of a community when faced by external pressures and stresses [25, 26]. SVI ranges from 0 to 100, where a value of 100 indicates the most vulnerable population. SVI will be estimated using zip code and will be categorized as low (lowest quartile), average (middle two quartiles) and high (highest quartile).	Baseline
	Payor	Medicaid/CHIP, Medicare, Commercial, Dually eligible, Other, Unknown	Baseline
	US region	Northeast, North Central, South, West, Unknown	Baseline

Variable type	Variable	Definition	Measurement period
	Index year	Calendar year of first HIV diagnosis code	Baseline
	Alcoholism	ICD-9-CM or ICD-10-CM codes listed in Annex Table 1.1	Baseline and follow-up
	Asplenia	CPT/Healthcare Common Procedure Coding System (HCPCS), ICD-10-Procedure Coding System (ICD-10-PCS), ICD-9-Procedure Coding System (ICD-9-PCS), ICD-9-CM, or ICD-10-CM codes listed in Annex Table 1.2	Baseline and follow-up
	Asthma	ICD-9-CM or ICD-10-CM codes listed in Annex Table 1.3	Baseline and follow-up
	Chronic heart disease	CPT/HCPCS, ICD-10-PCS, ICD-9-PCS, ICD-9-CM, or ICD-10-CM codes listed in Annex Table 1.4	Baseline and follow-up
	Chronic kidney disease and renal failure	CPT/HCPCS, ICD-10-PCS, ICD-9-PCS, ICD-9-CM, or ICD-10-CM codes listed in Annex Table 1.5	Baseline and follow-up
	Chronic liver disease	CPT/HCPCS, ICD-10-PCS, ICD-9-PCS, ICD-9-CM, or ICD-10-CM codes listed in Annex Table 1.6	Baseline and follow-up

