9.9. Limitations of the Research Methods

There are several limitations in this study. Given that this is an observational study using health care administrative claims data, residual confounding due to missing or unmeasured information is possible. To examine this, we will assess the effect of PCV13 on a negative control outcome and the effect of a negative control exposure on our outcomes of interest. If the HRs in any of these models are less than 1.0, it would indicate that residual confounding exists and may result in adjustment of our VE estimates.

Second, health care administrative claims data will be available from January 1, 2014 through September 30, 2022. The recommendation to vaccinate all PLWH was published in June 2012, and some PLWH may have received PCV13 prior to January 1, 2014 and be misclassified as unvaccinated. In addition, PLWH eligible for the study may have received PCV13 vaccination during a time period in which we do not have their claims data. Misclassification of PCV13 vaccine status may lead to lower estimates of vaccine effectiveness than in truth, because our unvaccinated cohort will incorrectly include vaccinated PLWH.

In addition, we are using ICD-9-CM and ICD-10-CM codes to define HIV infection. Our definition of HIV infection requires at least one HIV-related diagnosis code in the inpatient setting or at least two HIV-related diagnosis codes in the outpatient setting. While this definition of HIV has been used in previous administrative claims database studies, it is possible that these codes may be used by health care providers to order laboratory tests to rule out HIV infection and thus, some individuals without HIV will be included in our study population.

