### **5.2.1. Inclusion Criteria**

- 1. HIV infection defined as at least one inpatient International Classification of Diseases, Ninth Revision, Clinical Modification (ICD-9-CM) or International Classification of Diseases, Tenth Revision, Clinical Modification (ICD-10-CM) code related to HIV (Appendix Table 7.1) or ≥2 outpatient ICD-9-CM or ICD-10-CM codes at least 30 days, but no more than 730 days, apart during January 1, 2014 and December 31, 2021*

*AND*

- 2. At least 18 years of age at the time of the first recording of HIV-related ICD-9-CM or ICD-10-CM code*

*AND*

- 3. At least six months of continuous enrollment in medical and pharmacy plans after the first HIV-related ICD-9-CM or ICD-10-CM code between January 1, 2014 and December 31, 2021. A gap of 30 days or less in enrollment will be allowed during this six month period.*

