### 5.3. Variables

#### 5.3.1. Effectiveness Endpoints

The outcomes of interest for the primary and secondary objectives are listed in Table 5.2.

Episodes separated by at least 90 days will be considered independent events. For claims that include pneumonia that are separated by <90 days, those claims will be collapsed into a single episode with a date of the initial diagnosis.

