**Table 5.2 Outcomes of Interest**

Outcome Type	Outcome	Definition
Primary outcomes	IPD	ICD-9-CM or ICD-10-CM codes listed in Appendix Table 7.4
	Pneumococcal pneumonia	ICD-9-CM or ICD-10-CM codes listed in Appendix Table 7.4
	All-cause pneumonia	ICD-9-CM or ICD-10-CM codes listed in Appendix Table 7.4
Secondary outcomes	Pneumococcal pneumonia or pneumonia with unspecified causes	ICD-9-CM or ICD-10-CM codes listed in Appendix Table 7.5
	Pneumonia with unspecified causes	ICD-9-CM or ICD-10-CM codes listed in Appendix Table 7.5
Sensitivity analysis outcome	All-cause pneumonia not associated with HIV	ICD-9-CM or ICD-10-CM codes listed in Appendix Table 7.6

For combination diagnosis codes, (e.g., bacteremia + pneumococcus) for diagnoses in an inpatient setting patients must have all codes within the same admission. The latest date of the combination of diagnoses will be used as the diagnosis date. For diagnoses in an outpatient setting patients must have all codes within the same date.

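### Follow-up starts six months after the first HIV code, yet the HIV definition can be met later; for late-confirmed people entry depends on post-index events, with unknown direction and size of any VE bias

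*Protocol*

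**What the plan says.** Protocol 9.1 requires six months of enrollment after the first HIV-related code, calls that period baseline, and sets the start of follow-up by this rule: "The date following the last date of the baseline period will be defined as the index date". SAP 5.1 and 5.8.2 repeat it.

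The HIV definition is separate. Protocol 9.2.1 accepts one inpatient code, or two outpatient codes "at least 30 days, but no more than 730 days apart, during January 1, 2014 and December 31, 2021". SAP 5.2.1 has the same rule. Neither document says that the definition must be complete by index, or that follow-up starts when it is complete. The only exclusion (Protocol 9.2.2, SAP 5.2.2) concerns PCV13 before the first HIV code.

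Three other places bear on the point:

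- Protocol 9.1 gives a purpose for the baseline: "The baseline period was also selected to minimize the number of outcome events that existed prior to or triggered an HIV diagnosis".
- Protocol 9.3, Table 1, dates age by the year in which the person meets the HIV criteria, but dates index year by the first HIV code. The documents therefore treat these as two different dates.
- Protocol 9.9 says of HIV codes that "it is possible that these codes may be used by health care providers to order laboratory tests to rule out HIV infection".

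**The concern.** A cohort should be fixed by what is known on the day follow-up starts. Here a 730-day window is attached to a six-month baseline, so some people can enter on the strength of a code recorded after index.

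People whose first code is inpatient, or who complete the definition within baseline, are not affected. For the others, two things follow.

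- **Outcome creates eligibility.** A pneumonia or IPD admission that carries an HIV code can complete the definition and also be counted as an event.
- **Guaranteed time.** Anyone who dies, disenrolls or is not coded again before confirmation is left out together with their person-time. The early time that remains comes only from people who lived and stayed enrolled to confirmation.

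The first adds events and the second removes some fatal ones, so they can oppose each other. Either distorts VE only if late-confirmed people are vaccinated differently from others at the same follow-up time. For this group the baseline also misses its stated aim, because it is anchored to a code that may turn out to be a rule-out test.

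**Working it through.** **1. How late confirmation can be.** If the first code belongs to the qualifying outpatient pair, the second can fall 730 − 183 = 547 days after index. The text does not require the first code to be in the pair, and an inpatient code qualifies at any time. The theoretical limit is therefore 1 July 2014 to 31 December 2021, or 2,740 days. At-risk time also stops when enrollment ends.

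**2. Inputs for an illustration (all-cause pneumonia).** From Protocol 9.5: 175,000 people; rate 0.05487 per year; true VE 15% (HR 0.85); planned 95% CI 13 to 17 (Table 3, 97 months, 4% censoring). Total time is about 38,848 / 0.05487 = 708,000 person-years, using the Table 3 event count at VE 5%.

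The vaccinated share of events, p, is implied by the planned CIs: p(1 − p) = 1/(D × SE²), with D events and SE = [ln(1 − lower) − ln(1 − upper)]/3.92. At VE 15%, SE = [ln 0.87 − ln 0.83]/3.92 = 0.0120 and D = 38,176, so p = 0.24. The four 97-month CIs at 4% censoring give 0.16 to 0.24; I use 20% as the vaccinated share of person-time. The 36-month IPD CIs at 4% censoring give 0.11 and 0.13, so the sponsor's own figures suggest that vaccination accrues over follow-up.

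Assumed, because the documents give none of it: 10% of people confirmed late, a one-year window, and 20% of them with a pneumonia event in it (about 3.6 times the protocol rate).

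**3. Calculation.** The Cox model compares people at the same time since index, so year 1 is its own stratum. Late-confirmed people contribute 175,000 × 10% = 17,500 person-years and 3,500 events to it. Other people contribute 157,500, of which a share v is vaccinated. Later time is 708,000 − 175,000 = 533,000 person-years, with its vaccinated share set so that other people's time is 20% vaccinated overall. With events e and person-years t by vaccination status, the common HR h solves

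Σ over strata of [e_vac − (e_vac + e_unvac) × h·t_vac / (h·t_vac + t_unvac)] = 0.

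Example, v = 10% and late group unvaccinated:

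- Year 1: 735 events in 15,750 vaccinated person-years; 7,778 + 3,500 = 11,278 events in 159,250 unvaccinated person-years.
- Later: 5,706 events in 122,350 vaccinated and 22,532 in 410,651 unvaccinated person-years.
- h = 0.819, VE = 18.1%, a shift of +3.1 points.

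| Year-1 vaccinated share, others | Late group vaccinated alike | Half as vaccinated | Unvaccinated |
|---|---|---|---|
| 5% | 0 | +0.8 | +1.6 |
| 10% | 0 | +1.5 | +3.1 |
| 20% | 0 | +3.0 | +5.9 |

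With 1% confirmed late, the two right-hand columns run from about +0.1 to +0.7. With 10% late but 10% having an event, they run from about +0.3 to +1.9.

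**4. Cross-check by simulation.** A simulated cohort entered at index and kept only if confirmed later used the same rate, HR 0.85, 4% censoring and up to 97 months.

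- Where outcome admissions and vaccination visits both often supplied the confirming code (90%), VE shifted by +1.65 to +5.75 points (10% or 30% needing later confirmation).
- Where outcomes did not confirm but some were fatal, VE shifted by −0.14 (10% late, 8% fatal), −0.46 (30%, 8%) and −1.48 points (30%, 25%). The 8% is the minimum IPD case fatality in Protocol 7; the 25% is assumed.
- Where vaccination did not affect confirmation, the shift was about zero.
- Starting follow-up at the later of index and confirmation brought VE within about 0.2 points of the full-cohort value in all seven final scenarios.

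**The case against.** The strongest reply is that the plan already does much of the work. The six-month lag removes many outcomes that prompted a diagnosis, and Protocol 9.9 discloses false HIV codes. The age definition suggests that the criteria were expected to be met by index. Figure 1 might also show a rule that could not be seen. On this view, a statement of the rule and a count of late-confirmed people would be enough.

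Part of this stands. The lag shrinks the affected group, and the group may be small. Weighting may also help: any shift works through a vaccination imbalance, and ART adherence, CD4 and viral-load testing, physical exams and hospitalization are plausible correlates of late confirmation. A reader might infer that IPTW and IPCW do nothing here. The documents do not support that, and the illustration is unweighted, so it does not show the bias left in the planned analysis. But the weights are fitted among people already admitted and cannot restore those who never qualified.

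The negative control outcomes (SAP 5.8.8) may react to the same selection. They cannot separate it from confounding, and any correction is optional.

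Two larger figures are tempting. Pooling all follow-up under the same assumptions gives +3.3 (half as vaccinated) and +6.4 (unvaccinated), but that sets first-year vaccination against a 97-month average. Giving late-confirmed people no events at all gives −1.3 and −2.7, but guaranteed survival does not exclude non-fatal pneumonia, and such cases stay in.

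**Conclusion.** Followed as written, the plan makes cohort entry depend on post-index events for people confirmed late. The text supports that much, subject to Figure 1. It should be corrected.

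No VE shift is established. A reader might infer that VE is overstated, or that the error exceeds the planned CI half-width of about 2 points (13 to 17 at VE 15%). The documents support neither. The late-confirmed share, the window, the event frequency and that group's vaccination are all assumed, and the sign changes with them. At a 5% year-1 vaccinated share, even an unvaccinated late group moves VE by only 1.6 points; several points need a higher share together with an event-rich, under-vaccinated late group. The negative shift from lost fatal cases is likely small.

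The case for change is that the rule misses the protocol's stated aim, the size cannot be judged from the planned outputs, and a better rule is available from the same data.

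**What to change.** In Protocol 9.1 and SAP 5.1 and 5.8.2, redefine the index date as the later of:

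1. the day after the six months following the first HIV code; and
2. the day after the HIV definition is first met, meaning the second code of the first qualifying outpatient pair or discharge from the first inpatient stay with an HIV code.

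Require enrollment on that date. Changing only the start of counting would leave the old index in force elsewhere, so carry the new one through:

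- Protocol 9.7 (follow-up);
- SAP 5.3.2 (covariates from the six months before the new index);
- SAP 5.8.4 (weights);
- SAP 5.8.6 (person-time);
- the 0-3, 3-5 and 5-7-year clock.

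Take PCV13 status as of the new index. Do not count an outcome episode that began before it. SAP 5.3.1 says of pneumonia claims less than 90 days apart that "those claims will be collapsed into a single episode with a date of the initial diagnosis", so later claims folded into such an episode do not count either.

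In the SAP 5.8.9 subject evaluation table report, by PCV13 status, the number with a delayed index, the person-years removed, and the number of qualifying claims that carried an outcome code. Keep the current index rule as a sensitivity analysis.

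**Cost.** No new data. Weights must be refitted for each outcome, for first and recurrent events, and in each subgroup. With 1-10% confirmed late and a mean window of 0.5-1.5 years, the loss is 175,000 × 1% × 0.5 = 875 to 175,000 × 10% × 1.5 = 26,250 person-years, or 0.1-3.7% of 708,000. If that time is event-enriched (10% late, 10-20% with an event), 1,750-3,500 of 38,848 events go (4.5-9.0%), and the CI widens by 1/√(1 − 0.045) − 1 = 2.3% to 1/√(1 − 0.090) − 1 = 4.8%. If the programs already require confirmation by index, one sentence in Protocol 9.1 and SAP 5.8.2 settles the point.
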